### **Laboratory Testing**

***HIV and STI Testing:*** All methodology will be used from the parent study in order for us to conduct additional STI/HIV testing (after their participation with the parent study ends) with participants for our 12 month follow-up assessment and participants recruited outside of the parent study. We will use the Determine® test (Abbott Pharmaceuticals), which is licensed in Mexico. Blood specimens will be obtained by venipuncture, and centrifuged on site. A vaginal swab will be obtained by a trained nurse. We plan to use the same methodology, infrastructure (procedures for sending samples to the lab etc.), and staff as the parent study by providing funding to extend both infrastructure and staff of the parent study until our study has been completed. Notably, there will be some overlap, as the parent study will still be actively testing their final participants during some of our 12 month follow-up data collection (data collection took place over 12-14 months for the parent study cohort), and thus, the parent study staff will be actively conducting data collection.. Vaginal swabs will be batched and sent for gonorrhea and Chlamydia testing, since rapid tests for these pathogens lack sensitivity. All specimens will be labeled with the subject's ID# and date, batched and stored at -20 C in on-site freezers before being shipped weekly on ice to the San Diego for further STI testing. Staff have a 'Fastpass' and CDC border permit to facilitate shipping. Two serum aliquots will be shipped to the UCSD CFAR repository where they will be retained for potential future testing. Syphilis serology will be conducted using the rapid plasma reagin (RPR) test (Macro-Vue, Becton Dickenson, Cockeysville, MD, USA). All RPR-positive samples will have confirmatory testing using the *Treponema pallidum* hemagglutinin assay (TPHA) (Fujirebio, Wilmington, DE, USA). *Neisseria gonorrhoea* and *Chlamydia trachomatis* will be detected from vaginal swabs using Aptima® Combo 2 (Gen-probe, San Diego, CA), a direct target-amplified nucleic acid probe test. Reactive tests will be confirmed by a re-test.

***Pre- and Post-test counseling and referrals:*** As detailed above and in the sections below, we will follow the same protocols as the parent study in terms of the counseling and referrals conducted during the additional specimen collection (Participants from the parent study which are part of our study participate in one additional survey and specimen collection after their participation in the parent study ends. In comparison, participants recruited outside of the parent study participate in two additional survey and specimen collection.). Also, as described above, parent study staff trained in providing counseling and referrals will be hired to implement these activities for this additional assessment carried out for our study (at 12 months follow-up, which will correspond to a 24 month follow-up assessment for parent study participants). The same staff from the parent study will also conduct the additional assessments required for participants recruited outside of the parent study.

All participants will receive pre- and post-test counseling before and after their HIV and STI tests. Rapid test results for HIV will be ready within 20 minutes, at which time they will be read by a trained counselor and shared with the participant in a private room. Specimens testing HIV+ will be repeated with a second rapid test. All women will receive post-test counseling and those testing positive will be referred to a medical doctor at the local Municipal Health Clinic for follow-up, where free ARVs are provided for those with CD4 counts <300. Participants will be asked to return within one month to receive the remainder of their STI test results. If a participant does not return for her one month follow-up to receive test results, our team of outreach workers who are familiar with the target population will continue to follow-up with the

participant and try to locate the project participant based on the information provided on their locator form. Parent study staff (who will be hired to work with us for this final assessment) have been trained to be discrete in communicating with those listed on participants' locator forms, never mentioning specific results or eligibility criteria for participating in the health study. In cases of active syphilis (e.g., titers >1:8), gonorrhea, or Chlamydia, all subjects are eligible under Mexico Ministry of Health guidelines for free on-site treatment. Mexican guidelines for post-test counseling and STI treatment are identical to that of the CDC. New CDC guidelines recommending cephalosporins for gonorrhea treatment will be adhered to. We will provide referrals to municipal clinics when urgent medical attention is warranted. At each visit, women will be counseled to avoid self-medicating STI symptoms to avoid promoting resistance. Women will be encouraged to refer their sex partners (including clients) for free STI testing and treatment at the Municipal Health Clinics or other local clinics. To encourage women to return for STI treatment, women be given the choice of non-cash incentives, including toiletry items (e.g., shampoo, soap, sewing kits, feminine hygiene products), small toys for their children, baby food, taxi vouchers, not to exceed \$5 USD per visit.

### **Specific Aim 3: To assess ESTIMA in terms of quality of implementation, receptivity by participants, and capacity to be maintained by *Via* microfinance efforts**

ESTIMA will be monitored for satisfaction, receptivity, fidelity, and quality of program implementation. Because this is a preliminary implementation and assessment, Aim 3 will be extremely important for providing recommendations for future refinement and delivery of the ESTIMA project. Evaluation of satisfaction and receptivity will include: 1) post-training evaluation forms among staff (to be completed after implementation of each participant training session) to assess challenges or barriers during implementation of the trainings, aspects that went particularly well, overall satisfaction with the training, as well as any issues in the ethical conduct of the study, and 2) qualitative data collection (approximately 2 focus groups with 10 women in each per intervention group, and approximately 5 individual interviews per intervention group), as well as quantitative assessments (conducted during follow-up survey) among participants on satisfaction and response to program. During the last session, participants will be asked if they are interested to participate in a focus group as well as individual interviews that will ask about their satisfaction with the program. Focus group and individual interviews will take approximately 60-90 minutes; responses will be transcribed and translated. All data will be reviewed for themes specific to receptivity, barriers or challenges, quality, feasibility, and appropriateness. Reports will summarize both qualitative and quantitative findings.

Monitoring and evaluation of recruitment, random assignment, adherence to intervention design, retention of participants, contamination across arms, and the incidence of adverse events will include: 1) standard training and periodic observations for all intervention staff; 2) weekly meetings between intervention staff and the Program Director, in which intervention staff review difficult situations that have arisen and discuss these and possible solutions; and 3) quantitative data collection on program recruitment, delivery (e.g. whether all segments of the curricula were covered), potential contamination (e.g. number of control participants who report knowing women in the ESTIMA intervention) and retention. A final report will be developed based on this review to provide future recommendations regarding best approaches for program implementation as well as appropriateness of the intervention content.

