## **Phase II**

### **Specific Aim 2: To assess preliminary outcomes of ESTIMA**

**Recruitment and Random Assignment.** We will recruit ESTIMA participants from those who are completing 12 month follow-up for the parent study, using the same eligibility criteria and recruitment in Specific Aim 1 (assessing interest among those who indicate willingness to be recruited into a sub-study and based on responses in their surveys from the parent study), with an additional criteria related to women's drug use frequency; the specific criteria will be determined based on Aim 1 findings, consultation from the CAB and *Via* microfinance (drug use data will be retrieved from the parent survey; 41% and 53% of participants from the parent study report using drugs and alcohol less than once per week respectively). *Those who participated in Aim 1 and who fall within these eligibility criteria will be eligible for participation.* Research staff of the K01 and parent grant will work jointly to identify those willing and eligible during the 12 months follow-up data collection of the parent grant. From the parent study, we will recruit a total of 120 participants in expectation to afford a final sample size of at least 48 in each group (using a conservative estimate of 80% retention). Eligible and willing participants will be randomized to treatment assignment (ESTIMA or wait-list control group) using a randomizer software package, after enrollment. The microfinance groups of women (approximately 6-10 per group) will be formed and randomized to intervention or wait-list control condition. The wait-list control group will be provided with referrals to local FSW support organizations, as the standard of care (STI/HIV testing and referrals), and will receive ESTIMA subsequent to the 12 month follow-up data collection. ESTIMA will involve groups of approximately 6-10 women each; groups will initiate once sufficient numbers are enrolled (i.e. groups will be staggered in terms in initiation).

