Survey/Specimen Data Collection. The survey is expected to take approximately 45 minutes and approximately 30 minutes for STI/HIV testing; overall, with waiting times, we expect this aspect of study participation to take approximately 90 minutes. For the baseline ESTIMA survey and HIV/STI testing, we will use data collected from the parent study's 18 months follow-up survey and specimen collection. Participants recruited outside of the parent study will be provided with the survey and STI testing, and reimbursed for their time in the amount of \$30 (at baseline and 12 month follow-up) and \$20 at 6 month follow-up (survey but no STI testing). All participants will also complete a 5-10-minute supplemental survey during informed consent or at another time preferred by the participant and will measure greater details on women's alcohol use frequency and experiences of discrimination; these measures were not asked in the parent study survey but will be important to examine in terms of assessing intervention impact. For the ESTIMA 6 month follow-up, we will use survey data collected from the same survey as implemented at baseline (including the additional questions on alcohol use frequency and experiences of discrimination). Final 12 month follow-up for ESTIMA will be conducted independently of the parent study.. (We have budgeted for the costs associated with testing of ESTIMA participants for the 6 and 12 month follow-up, whereas the baseline will be conducted under the parent study. Trained research assistants arrange a follow-up interview time to be conducted at the study office via contact information collected as part of the parent grant. After providing informed consent, participants complete a 60 minute interviewer-administered survey using computer assisted personal interviewing (CAPI) (NOVA software, MD, USA). The survey (and any new items for the ESTIMA project) will be translated into Spanish, back-translated to English and reviewed for accuracy by the bilingual project coordinator and project consultants, who have also reviewed questions for cultural and linguistic appropriateness. Women will be reimbursed \$30 for the survey and testing (at baseline and 12 month follow-up) and \$20 at 6 month follow-up (survey but no STI testing). Data collection interviewers will not be aware of women's treatment assignment. Women who test positive for any HIV/STI test will be provided with appropriate treatment and/or referral to HIV care services. A participant tracking system will be developed during enrollment for the ESTIMA project in order to collect follow-up data (which will take place at the same study office) and kept up to date with information on address, phone number, etc., and all contact attempts. Permission to use different tracking methods (e.g. contacting friends) will be obtained at enrollment and kept current in order for us to collect the additional assessment after participants' involvement in the parent study ends (our 12 month follow-up). A key study aim is to identify retention challenges, which will be monitored quantitatively and qualitatively (Aim 3). Given that we are recruiting from the 18 month follow-up of the parent study, we also expect to recruit women who have a low probability of attrition, given that they were already among those not lost to follow-up for the 18 month data collection of the parent study. While we will use the parent study's 18 month follow-up data, we do not expect to see reductions in our outcome measures of interest until 12 months follow-up. However, 6 month follow-up may be useful to conduct mediational analyses to understand patterns in or variations of change in the outcome variables.

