sexual health risk indicators). The distributional properties and reliability of continuously scaled variables will be examined. Effects of the intervention on both intermediate and long-term outcomes (see Figure 1) will be examined using logistic regression analyses for dichotomous variables (e.g. GBV, consistent condom use) and ANCOVA for continuous variables (e.g. collective efficacy scales, income, number of sex trades). Analyses will focus on outcomes at the 12 month follow-up. ANCOVA using ranks will be used to examine outcome variables with non-normal distributions, such as income. While ESTIMA is powered to focus on intermediate outcomes, we will also investigate trends on longer term outcomes as well (Figure 1). We expect low rates of loss to follow-up, as ESTIMA is incorporated into existing *Via* trainings; however, we will track any participants who drop out of the program (Aim 3), as well as loss to follow up. If there is more than a trivial amount of missing data, we will examine whether there are any patterns in missing data by relevant study variables (e.g. violence experiences, demographic characteristics etc). Power calculations were performed using a significance level of 0.05 and 80% retention (n=48 in each group), with focus on **primary intermediate outcome variables** (economic security and collective power variables) (Figure 1). For analysis focused on variables of income and debt, number of sex trades, as well as the scales measuring women's collective power, we will have 80% power to detect a standardized effect size of 0.5, which is considered a moderate effect size based on work from Cohen (1988). We believe that a moderate effect size would be needed in order to ensure that the effect of the intervention is significant for wide-scale adoption and sufficient impact. However, because we will have small numbers for this pilot of the ESTIMA project, we recognize that we may only be able to find trends to report, and which will be used to secure further funds to run a full-scale trial. While we have not powered the trial to detect a significant effect on GBV, HIV risk behaviors, or HIV/STI, we anticipate a trend toward decreased reports of these in the intervention group compared to the control arm. Furthermore, collecting information on GBV, HIV risk, and HIV/STI will also provide information to power a subsequent larger-scale evaluation.

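### The only stated invitation to the Aim 3 focus groups and interviews comes at the last session, so women who stop attending earlier fall outside the qualitative sample on retention

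*Combined protocol and SAP*

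**What the plan says.** **Entry to the qualitative work.** Section 9, Specific Aim 3, states: "During the last session, participants will be asked if they are interested to participate in a focus group as well as individual interviews". The planned volume is "approximately 2 focus groups with 10 women in each per intervention group, and approximately 5 individual interviews per intervention group". No other route is described there or in the Specific Aims (Section 6).

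**The aim it serves.** Under Aim 2, Survey/Specimen Data Collection, the plan says: "A key study aim is to identify retention challenges, which will be monitored quantitatively and qualitatively (Aim 3". Aim 3 itself covers satisfaction, receptivity, barriers, feasibility and appropriateness, and is meant to guide refinement of the programme.

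**What is planned for women who leave.** The analysis text under Aim 2 says that "we will track any participants who drop out of the program (Aim 3), as well as loss to follow up". The monitoring paragraph of Aim 3 lists retention among the items of quantitative data collection. Neither mentions asking for reasons.

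**Other sources of feedback.** Aim 3 plans participant questionnaires, "as well as quantitative assessments (conducted during follow-up survey) among participants on satisfaction and response to program". It also plans staff forms after each training session "to assess challenges or barriers during implementation of the trainings", and "weekly meetings between intervention staff and the Program Director, in which intervention staff review difficult situations that have arisen". Section 15 adds close monitoring of loan repayment. Section 16 adds monitoring for loss of confidentiality in the first cohort and throughout.

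**The concern.** A woman who has stopped coming is not in the room when the invitation is made. The rule therefore selects on the very thing that the plan wants to understand. Those best placed to explain why the programme did not work for them are outside the stated sample, and those who stayed are likely to be more content with it.

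This matters because Aim 3 is the basis for refining ESTIMA and for planning a larger trial. Sections 14 to 16 name problems that could plausibly lead a woman to leave: pressure to take more clients to repay the loan, others taking the loan money, and becoming known as a sex worker through the group. The plan also staggers the groups so that problems in early groups can be corrected before later ones start. That safeguard works less well if the in-depth accounts come from those who stayed.

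**Working it through.** The question is who can enter the qualitative sample. Most of the check sets the text side by side; the arithmetic only gives the size.

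**1. The plan's own retention figure.** Inputs: 60 women per arm (Section 6) and 80% retention (Section 9, Aim 2).
- Retained: 60 × 0.80 = 48 per arm, which matches the plan.
- Lost: 60 × 0.20 = 12 per arm.

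This 80% is retention in study follow-up. It is not programme attendance, so the 12 cannot be read as the number who miss the last session.

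**2. Women outside the invitation.** The programme drop-out rate d is not stated, so a range is assumed. Number outside = 60 × d.

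| Assumed d | Women of 60 outside the invitation |
|---|---|
| 10% | 60 × 0.10 = 6 |
| 20% | 60 × 0.20 = 12 |
| 30% | 60 × 0.30 = 18 |
| 40% | 60 × 0.40 = 24 |

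The plan says "ESTIMA will involve groups of approximately 6-10 women each". At d = 20% this is 6 × 0.20 = 1.2 women in a group of 6 and 10 × 0.20 = 2 in a group of 10.

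**3. Does another planned source record why women leave?**

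| Source | What it can show about early leavers | What it leaves open |
|---|---|---|
| Tracking of drop-outs, retention data, missing-data patterns | How many left, and who | Why |
| Staff forms and weekly meetings | Barriers as staff see them | The absent woman's own account |
| Follow-up survey on satisfaction and response | Views of leavers who still attend follow-up | No reason-for-leaving item is stated; leavers lost to follow-up are not reached |
| Repayment and confidentiality monitoring | Loan and disclosure problems that come to light | Other reasons for leaving |

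Each source covers part of the ground. None is described as a qualitative account from a woman who left.

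**4. Focus-group numbers.** Two focus groups of 10 need 2 × 10 = 20 women.
- If "intervention group" in the quoted text means one microfinance group, 20 women cannot come from 6 to 10.
- If it means the arm, 20 of 60 is feasible, and the interviews number about 5 in all. Under the other reading they would number 5 × 6 = 30 (six groups of 10) to 5 × 10 = 50 (ten groups of 6).

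The analysis text under Aim 2 uses the term for the arm, and Section 6 sets the focus groups at two or fewer. The count therefore needs a clarification only.

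**The case against.** The strongest reply is that the plan never says completers only. That there is no other route is read from silence. Section 6 places the qualitative work with intervention participants, and Section 20 pays intervention participants for an in-depth interview on benefits and challenges; neither is limited to those who finish. A woman who leaves the programme but stays in follow-up still answers the survey's satisfaction questions, and several other channels pick up barriers. The sentence on retention challenges also sits in text about tracing women for follow-up data, so it may mean retention in the study more than attendance at sessions.

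Much of this stands, and it rules out some stronger readings:

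- A reader might infer that drop-outs are never asked why, or that the trial cannot identify barriers to retention. The documents do not support this. The survey items are not shown, so whether they touch on leaving is unknown, and the staff and monitoring channels will identify some barriers.
- A reader might infer that none of the 12 women per arm implied by 80% retention could enter the qualitative sample. That does not follow, because a woman lost by month 12 may have attended the last session.
- A reader might assume that women with repayment difficulty are excluded. Nothing in the rule says so; they may well attend the last session.
- It is tempting to express the bias as an inflated percentage of women who find the programme acceptable. The focus groups and interviews are read for themes and estimate no such percentage.

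What the reply does not remove is that staff who follow the plan will invite women at the last session, and no written step brings in those who left before it.

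**Conclusion.** The point holds as a gap in the stated selection rule. As written, the qualitative sample omits women who stop attending before the last session, and no procedure for recording their reasons is described. Qualitative evidence on retention would come mainly from last-session attenders and staff, with the other sources filling the gap in part.

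The size is uncertain: 6 to 24 of 60 intervention women for an assumed programme drop-out of 10% to 40%. The direction, a more favourable picture of the programme, is likely but rests on the assumption that leavers are less content than stayers. No sample-size or power figure is affected. This is a worthwhile and inexpensive improvement, and it does not invalidate Aim 3.

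**What to change.** In Section 9, Specific Aim 3:

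1. Make all women allocated to ESTIMA eligible for the individual interviews, whether or not they attend the last session.
2. Offer some of the interviews already planned to women who stopped attending. Contact them through the tracking system set up at enrollment and pay the $20 already given in Section 20.
3. State in the consent form that such contact may be made, since permission for tracking is now described in connection with collecting follow-up data.
4. Add a reason-for-leaving item to the follow-up survey for women who left the programme.
5. Report early leavers' answers separately from those of last-session attenders.
6. State whether the focus-group and interview numbers apply to each microfinance group or to the whole arm. This also settles how many interviews are available to share out.

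The cost is protocol wording, one survey item, some tracking calls and possibly a small consent amendment with ethics review. No extra interviews are needed. Women who left may be hard to reach, so some of the offered slots may go unfilled; reporting how many were approached and how many agreed would itself inform the aim on retention.
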